#### Spelling

#### Treatment of the PGC mechanism (PGC intervention)

For the PGC intervention, patients will receive language therapy of either phoneme-grapheme correspondence (PGC) or study of particular words (lexical therapy) or other similar type of therapy depending on the particular spelling deficit of each patient. Up to 30 English sounds will be selected representing most common word-initial English phonemes (speech sounds). Then a set of up to 30 English words starting with these sounds will be used as prompts to help the participants relate each sound to a grapheme (abstract letter identity or sequence of letter identities). In the case of spelling therapy with words, sets of up to 50 English words with matched psycholinguistic characteristics (frequency, length etc) will be chosen and divided in sets for either baseline testing, training, homework, or repetition. In the case of PGC therapy, the participant will be either asked to provide the letters that would correspond to each sound and if failed to do so will be provided with word prompts. In the case of lexical therapy, the participant will be asked to spell the chosen words and if failed to do so will be taught the spelling of each word in the training set or proceed to the rest of the set in other sets. Words or PGCs will be taught in blocks of 10; when the patient reaches criterion (80% correct) he or she will continue to the other blocks. Individuals who reach criterion quickly will move to a second stage, in which they will be asked to write words beginning with each target phoneme. They will be assisted in correcting the spelling of the words by "sounding out" the word. Baseline evaluation before each therapy session will be held before each therapy session and will either require that the participant would choose--from a series of possible initial letters or letter sequences of English written in front of him or her--the letter or letter sequence that corresponds to the phoneme the examiner provides each time. Treatment of the lexical access mechanism (lexical access intervention).

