For the lexical access treatment we will follow the methodology of the only other published spelling intervention in PPA (Rapp & Glucroft, 2009). Stimuli will consist of three word sets (n=10 for each set) that will be matched for lexical frequency, letter length, regularity, and concreteness. We will use 10 stimuli for each set to better match the PGC and lexical treatments. Set 1 will serve as trained items for the first condition (either sham or tDCS), and set 2 as untrained items and then set 2 will serve as trained items JHMIRB eFormA 01

and set 3 as untrained. A spell-study-spell procedure (Beeson et al., 2013; Rapp & Glucroft, 2009) similar to that used in a number of other studies will be applied to the trained words, such that at every training session the patient will be asked: (1) to spell each word to dictation, (2) to study the word presented on a written note card and orally name each of its letters while the experimenter repeats the word, and (3) if the word has been spelled incorrectly to attempt to spell it again. This procedure will be repeated until the words of each set are correctly spelled for two consecutive sessions. If a word is spelled correctly on the first attempt, the word will still be presented for the participant to study and only then will the experimenter continue to the next word. Untrained words will be presented for spelling to dictation only at the time of the pre- and post-treatment evaluations and at two follow-ups to evaluate whether therapy gains generalize to the spelling of other words.

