#### Assessment

Follow-up assessment will probe all sets of trained phoneme-grapheme correspondences, words, or other stimuli (e.g. sentences) to identify whether or not the patient has retained knowledge of the trained items. We will look at generalization effects (i.e. effects of training to untrained items). Differences in baseline measures in pre- and post-therapy accuracy for phoneme-grapheme correspondences for each patient will be evaluated using chi-square or Fisher's exact tests.

Participants will receive approximately 3-5 therapy sessions per week for 1-3 weeks for each stimulation site. There will be 1-5 stimulation sites depending on the characteristics of each individuals and their availability.

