#### tDCS methods:

Participants will take part in 5-15 consecutive training sessions (3-5 per week), each with a different tDCS condition/site of stimulation (see Table 1) separated by 2 months. Three pre-training sessions separated by 2 weeks, each with a different tDCS condition/site of stimulation (see Table 1), may be proposed to pre-test the tDCS montages. Anodal tDCS has typically been shown to up-regulate neuronal excitability and produce enhancement of behavioral performance. We hypothesize that anodal cerebral tDCS applied during behavioral therapy will enhance the therapeutic outcome relative to the sham tDCS condition as measured by the change from pre- to post-treatment accuracy in the trained task (e.g. number of correctly learned grapheme-phoneme correspondences, correctly named pictures, correctly named words in a given category) for trained and untrained stimuli. Previous tDCS protocols for acquisition of eyeblink

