conditioning using tDCS have received Johns Hopkins IRB approval. We will use either the same equipment as [name] and his team have used (a Chattanooga lonto Device) as well as the same application technique, recently acquired state-of-the-art device using special software for doubleblinding (Soterix 1x1 CT: clinical trials), or a Neuroelectrics Starstim 8 device, which is a high-definition tDCS cap with higher precision. In order to administer intervention during the global pandemic and in a virtual manner, we will offer the option of remote stimulation (Soterix mini-CT device and MIND STIM+, YBrain). Attached please find letters from Clinical Engineering documenting that the tDCS devices have undergone clinical inspection as well as the manuals. When remote devices are implemented, participants and spouses will be trained prior to intervention and sessions will be conducted in real-time via video conference (e.g., Zoom). Stimulation will be delivered at an intensity of 1-2mA (estimated current density 0.04 mA/cm2; estimated total charge 0.048C/cm2) for a maximum of 20 minutes in the tDCS groups and for a maximum of 30 seconds in the Sham group. For both interventions (tDCS and Sham) the electrical current will be increased in a ramp-like fashion at the onset of the stimulation eliciting a transient tingling sensation on the scalp that usually disappears over seconds. Although the ramping process requires the researcher's input, it is now feasible to blind study staff who will be applying tDCS, as well as participants, as we now have a box that allows another member of the team to set the box to "tDCS" or "sham" without the knowledge of the researcher providing the therapy. In the Starstim 8 and remote devices, double-blinding is achieved through codes known only to the PI who is not administering any stimulation or evaluation, so both the technician or professional who administers the stimulation and evaluation are blind to the current condition being either actual tDCS or sham. After the ramping, in the sham condition, the intensity drops to 0 mA. These procedures have been shown to successfully blind participants as to whether they were members of experimental or control groups (Gandiga et al., 2006). The sites of tDCS application will be determined by the type of therapy used and the PPA variant group or MCI and will be either the inferior frontal gyrus (IFG), the supramarginal gyrus (SMG), or the middle temporal gyrus (MTG) or a combination as shown in the literature. A recent meta-analysis of the functional neuroimaging literature on spelling has not yet identified clearly the neural substrates for PG conversion; the most plausible network includes the inferior parietal lobule including the supramarginal gyrus (Purcell et al., 2011). This area has also been identified as a critical area for spelling in the lesion literature as well. Another plausible area that shows activations during both PG conversion and lexical (word) spelling is the inferior frontal gyrus (IFG) (Purcell et al., 2011) and lesions in the IFG are associated with impaired PG conversion (Beeson et al., 2010). The stimulation site of IFG will be determined between F7 and F8 electrodes and that of SMG between TP3 and TP4 using the EEG 10-20 electrode position system (Homan, 1988). Additionally, studies have reported positive results of tDCS over the left dorsolateral prefrontal cortex (DLPFC) leading to improvement in attention deficits due to stroke, Parkinson's disease, and major depression (Boggio et al., 2006, 2007; Fregni et al., 2006; Kang et al., 2009). In addition to improving attention, anodal tDCS at the left DLPFC has been shown to improve working memory in TBI patients (Ulam et al., 2015). We hypothesize that anodal tDCS over the L DLPFC when administered in combination with cognitive training will improve language performance of PPA and MCI participants more than behavioral therapy alone, and that improvements may generalize to some other cognitive functions. The dependent variable will be the same baseline and post-therapy evaluation as described above that will take place before, after, 2 weeks and 2 months post-stimulation for each stimulation condition (see Table 1). These same areas, predominantly on the left, are activated during naming (Jarso et al., 2013) and working memory (Philipose et al., 2007). In most cases of PPA and all cases of MCI, we will stimulate areas of the left hemisphere that are not atrophied. In the most advanced cases of PPA, with severe left hemisphere atrophy, we will stimulate the same sites in the right hemisphere in order to stimulate its compensatory mechanisms (see Hypothesis 1d). By this design we will be able to achieve a within-subject design for all conditions as well as to evaluate immediate, short- and long-term effects of each stimulation site without confounds and without any carry-over effects. We will also conduct a 6-month language evaluation to assess the overall therapy gains.

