#### 6. Study Statistics

#### *a. Primary outcome variable.*

The primary outcome measures will be: a) change in performance from pre- to post-treatment levels on the trained items (e.g. change in % accuracy in phoneme-grapheme conversion of trained phonemes, % accuracy naming of trained pictures, average % correct names produced in trained categories in 1 minute), and, b) generalization to untrained items, measured by change in performance from pre- to post-treatment levels on the trained items (e.g. change in % accuracy in phoneme-grapheme conversion of untrained phonemes, % accuracy naming of untrained pictures, average % correct names produced in untrained categories in 1 minute). For those individuals with DLPFC stimulation for executive functions, we will use an additional automated score from BrainHQ program training (Smith et al., 2009). For individuals

receiving home-based tDCS over the left perisylvian areas and their right hemisphere homologs, we will assess pre- to post- language scores.

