## c. Statistical plan including sample size justification and interim data analysis.

Design. This is a crossover trial, where each participant will be randomly assigned to receive either "IFG tDCS, then sham then SMG (in case a second stimulation site is implemented)" (group1) or "SMG then sham then IFG" or "sham then IFG then SMG". In case a second stimulation site is not implemented participants will receive either sham and then tDCS (group 1) or tDCS and then sham (group 2). Based on previous studies regarding long-term effects of tDCS (see Fiori et al., 2011; Fridriksson et al., 2011; both looking at 3-weeks post-stimulation in participants with aphasia) and given the degenerative nature of PPA (and some cases of MCI), we assume that even though the effect of tDCS on the absolute level of the outcome may or may not persist at 2 weeks, the effect on the rate of decline persists no longer than 2 weeks. Analyses. The primary analyses will be a robust type of repeated measures Multivariate ANCOVA. Specifically, for each subject (i) and at follow-up times t=immediately after treatment, then 2 weeks and 2 months, we will consider the data  $IFG_{ti}$ ,  $SMG_{ti}$ , and  $S_{ti}$ ; here,  $IFG_{ti}$  is the change of outcome from just before IFG tDCS treatment to time t after IFG tDCS treatment for subject i; and similarly for SMGt,i, and St,i for IFG tDCS and sham. For the behavioral methods, change of outcome is considered the difference (before and after therapy) of the independent measure of initial letter-sound associations learned. Then the research hypothesis that IFG (or SMG) treatment is superior to sham will be tested by testing the hypotheses that the distribution  $pr(R_{ij} - S_{t,i})$  (or  $pr(L_{t,i} - S_{t,i})$ ) is not centered at zero. This will be done nonparametrically by obtaining the latter null distributions by the random permutation of the treatment labels (IFG, S, SMG) of the data for each patient (Rosenbaum, 1988). The design effect, i.e., the ratio of sample sizes needed by an independence design vs. the crossover design to achieve a given power, depends on the correlations of outcomes across times and treatments. We have calculated that this crossover design with 30 participants and design effect of 1.5 has power 75% to detect an effect size of 0.8 between a tDCS site and sham treatment. In secondary analysis, we will use regression to examine if any effects of tDCS vary across participants with different characteristics such as age and atrophy volume. The present design allows us to evaluate the language and neuromodulatory effects of both IFG and SMG stimulation as well as language therapy alone (in the condition of sham stimulation).

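### Section 6c scores the primary analysis on letter-sound associations alone, while section 6a and the tDCS methods score each participant on the task trained

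*Combined protocol and SAP*

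**What the plan says.** Section 6c sets up the primary analysis as within-patient comparisons of change under each stimulation site with change under sham, tested by permuting treatment labels. It then says what change means for the behavioral methods: "change of outcome is considered the difference (before and after therapy) of the independent measure of initial letter-sound associations learned". It gives no other behavioral score.

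Section 6a lists two primary measures, change on trained items (a) and generalization to untrained items (b). Beside phoneme-grapheme accuracy, its examples for (a) include "accuracy naming of trained pictures, average % correct names produced in trained categories in 1 minute". It adds a BrainHQ score for participants stimulated over the DLPFC and language scores for home-based participants.

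The tDCS methods in section 3a also use accuracy in the trained task, for trained and untrained stimuli, with examples "number of correctly learned grapheme-phoneme correspondences, correctly named pictures, correctly named words in a given category". They later add: "The dependent variable will be the same baseline and post-therapy evaluation as described above".

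**The concern.** Section 6c is where an analyst would look for the variable to put into the test. Read literally, it sends everyone to a letter-sound score. That is the target of one therapy stream (phoneme-grapheme correspondence), whereas the trial also gives lexical spelling, naming, repetition and computerized therapy. It also drops untrained items, which 6a(b) lists as primary.

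Two things are at stake. Participants trained on something else would have no usable score in the primary test, which would then rest on an unstated subset of the 30 used for power. And with two definitions in one plan, either could be reported as the planned one after results are seen.

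**Working it through.** **Step 1. The two definitions side by side.**

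| | Section 6c | Section 6a and tDCS methods |
|---|---|---|
| Score | Letter-sound associations | Accuracy on the task trained |
| Therapy streams | All behavioral methods, unqualified | Follows the therapy given |
| Untrained items | Not mentioned | Included |
| Offered as an example? | No | The specific tasks are examples of a general rule |

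Reading behavioral as simply the opposite of imaging does not help, because it widens the sentence to every stream. Reading the 6c measure as a common test for all still contradicts 6a.

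**Step 2. Who would have a letter-sound score (section 3a).**

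- Phoneme-grapheme therapy: yes. The probe asks for "the letter or letter sequence that corresponds to the phoneme the examiner provides each time".
- Word spelling: unclear. That probe stands in a paragraph covering both phoneme-grapheme and word therapy. The lexical access treatment itself uses word sets ("Set 1 will serve as trained items for the first condition (either sham or tDCS").
- Naming: none scheduled. Pictures and category words are trained and tested.
- Repetition: none scheduled. Triplets of words or sentences are trained and tested.
- Computerized therapy: none described.

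**Step 3. The plan's power figure.** Inputs from 6c: 30 participants, design effect 1.5, effect size 0.8. Alpha is not stated; two-sided 0.05 is assumed. The design effect is the independent-design sample size divided by the crossover sample size, so 30 × 1.5 = 45 equivalent participants, or n = 22.5 per arm. With noncentrality 0.8 × √(n/2) = 2.683, 2n − 2 = 43 degrees of freedom and critical value 2.017, power is 74.6% (76.5% by normal approximation). The stated 75% reproduces and is not in error. It takes all 30 as informative on one score.

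**Step 4. Illustration if only a share s have a letter-sound score.** The documents give no shares; these are assumed. Per-arm n = s × 45/2.

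| s | n per arm | Noncentrality | Power |
|---|---|---|---|
| 1 | 22.5 | 2.683 | 74.6% |
| 0.75 | 16.875 | 2.324 | 61.5% |
| 0.50 | 11.25 | 1.897 | 44.0% |

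**Step 5. Cost of one way to combine therapies.** Under 6a the plan still does not say how phoneme-grapheme, picture and category scores enter one permutation test. One option divides each tDCS-minus-sham difference by the root mean square of those differences within its therapy type. Simulation used one site, 30 participants and a mean difference of 0.8 × √(22.5/2)/√30 = 0.49 standard deviations. With equal spreads:

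- Three types (10/10/10 or 15/10/5): raw sum 73.4–73.8%, scaled 72.2–72.5%, a cost of about 1 point.
- Five types of six: raw 73.0%, scaled 70.2%, a cost of about 3 points.

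With three types whose spreads differ up to threefold, scaling recovered about 5 to 8 points.

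**The case against.** The strongest reply is that 6a carries the heading for the primary outcome, gives naming participants an explicit score, and so governs; the 6c sentence is leftover text. Much supports this. The Assessment part of section 3a says: "Follow-up assessment will probe all sets of trained phoneme-grapheme correspondences, words, or other stimuli (e.g. sentences"). Section 3b tests practiced and unpracticed items. It stands as the likely intent. But 6c specifies the analysis, nothing ranks 6a above it, and 6a alone does not say how therapies are combined.

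Stronger readings are tempting and should be resisted:

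- **That lexical spelling participants also lack a score.** The letter-sound probe may reach them, so the firm statement covers naming and repetition only.
- **That Assessment repeats the restriction.** It does say "pre- and post-therapy accuracy for phoneme-grapheme correspondences for each patient will be evaluated", but by chi-square or Fisher tests within each patient, which is not the group primary analysis.
- **That power is really 62% or 44%.** This needs assumed shares and a literal reading that the rest of the plan makes unlikely.
- **That the three follow-up times and a second site inflate the error rate.** 6c names a repeated measures multivariate analysis and does not clearly plan separate tests, so no familywise figure belongs to this point.
- **That the plan implies a single primary contrast on trained items.** 6a and Hypothesis 1a name untrained items as well.

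**Conclusion.** The contradiction is in current text and is wrong as written: followed to the letter, 6c leaves naming and repetition participants without a usable primary score and omits one of the two measures that 6a calls primary. It should be fixed before analysis. The conclusion rests on comparing the sections and needs no numerical assumption.

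The size in practice cannot be computed, because the number of participants per therapy is not given. The 62% and 44% figures are illustrations and do not carry the severity. If 6a is followed, as is probable, what remains is freedom to choose between two scores and an unstated rule for combining therapies.

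**What to change.** 1. In 6c, replace the letter-sound sentence with: change of outcome is the pre- to post-treatment change on the participant's own trained items (6a(a)) and, separately, untrained items (6a(b)), for the therapy received.
2. In 6a(b), correct the measure of generalization to change on the untrained items. The text says trained, although its own examples are all untrained.
3. State whether home-based and DLPFC or computerized participants enter this analysis and, if so, that they use the scores 6a names for them.
4. State before unblinding how scores from different therapy types are combined in the within-patient permutation test. Scaling by therapy-type spread is one option. If it is used, keep the types few and report raw change by type beside it, since the scaled statistic is not in percentage points.

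Whether to name a single primary contrast, and any multiplicity rule, is for the sponsor to decide.

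The cost is wording in 6a and 6c plus decisions on items 3 and 4. Trained and untrained items are already scheduled for testing, so no visit or test is added. Scaling, if chosen, costs the 1 to 3 points of power shown above when spreads are equal.

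### If a second stimulation site is used, permuting all three labels makes each site-versus-sham test depend on the site not being tested

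*Combined protocol and SAP*

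**What the plan says.** All of this is in section 6c, the statistical plan. If a second site is implemented, each patient is randomised to one of three orders of IFG, sham and SMG; otherwise each patient receives sham and one tDCS condition. For the three-condition version, "the research hypothesis that IFG (or SMG) treatment is superior to sham will be tested by testing the hypotheses" that the within-patient difference from sham "is not centered at zero". The formulas there use symbols other than the IFG and SMG just defined; I read them as those two conditions.

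Both nulls come from "obtaining the latter null distributions by the random permutation of the treatment labels (IFG, S, SMG) of the data for each patient". Nothing limits the shuffle to the two labels in a given comparison. The only description of the model is a robust repeated-measures multivariate ANCOVA. No permuted statistic, significance level or SD is given.

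The sample size statement is that "this crossover design with 30 participants" and a design effect of 1.5 "has power 75% to detect an effect size of 0.8 between a tDCS site and sham treatment".

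**The concern.** The plan asks two separate questions, whether IFG differs from sham and whether SMG differs from sham. The null for the first says nothing about SMG. Shuffling three labels within a patient nevertheless treats SMG as exchangeable with both, so SMG's mean and spread enter the reference distribution for IFG minus sham. The same holds the other way round.

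The protocol does not expect the three conditions to be equal. Hypothesis 1c predicts gains specific to the stimulated region, and the Background expects generalisation to depend on the area stimulated. One site working while the other does not is a result the trial is meant to detect, and there the three-label null is wrong for the other site's test. At stake is a primary p-value for one site that moves because the other site worked well, or was noisy.

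**Working it through.** **The plan's own figure.** A design effect of 1.5 turns 30 crossover patients into 30 × 1.5 = 45 independent patients, or 22.5 per arm. For effect size 0.8 at two-sided 5%, power ≈ Φ(0.8 × √(22.5/2) − 1.96) = Φ(2.683 − 1.960) = 76.5%; the noncentral t gives 74.6%. The stated 75% reproduces. One-sided 5% gives 85.0% and two-sided 2.5% gives 67.1%, so I take two-sided 5% per comparison as the working assumption.

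**Inputs.** From section 6c: n = 30, the three labels and the two pairwise hypotheses. Assumed because the documents are silent: SD 1 for the IFG (I) and sham (S) change scores; a range of SDs and shifts for SMG (M); common correlation ρ. Values of 0 and 0.5 are illustrative. The value -1/3 follows if the design effect is read as 2/(1 − ρ) = 1.5.

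**Formula.** Under the three-label shuffle, a patient's permuted difference is ±(I−S), ±(I−M) or ±(S−M), each with probability 1/6. When the pairwise null I = S is true:

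- V_ref = [E(I−S)² + E(I−M)² + E(S−M)²] / 3
- V_true = E(I−S)² = 2 − 2ρ
- large-sample level ≈ 2[1 − Φ(1.96 √(V_ref / V_true))]

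**Level of the IFG-versus-sham test, raw mean difference, nominal 5%.** Simulations used 30 patients, thousands of trials per scenario and 599 or 999 permutations.

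| SMG relative to sham | ρ | V_true | V_ref | Formula | Simulated |
|---|---|---|---|---|---|
| Same mean and SD | 0 | 2 | 2 | 5.0% | 4.9% |
| Shift 1, SD 1 | 0.5 | 1 | (1+2+2)/3 = 1.667 | 1.1% | 1.2% |
| Shift 1, SD 1 | -1/3 | 2.667 | (2.667+3.667+3.667)/3 = 3.333 | 2.8% | – |
| No shift, SD 1.5 | 0 | 2 | (2+3.25+3.25)/3 = 2.833 | 2.0% | 2.3% |
| No shift, SD 0.7 | 0.5 | 1 | (1+0.79+0.79)/3 = 0.860 | 6.9% | 7.0% |
| No shift, SD 0.5 | 0 | 2 | (2+1.25+1.25)/3 = 1.500 | 9.0% | 8.8%, 9.1% |
| Shift 0.8, SD 0.5 | 0 | 2 | (2+1.89+1.89)/3 = 1.927 | 5.4% | 5.4% |

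Swapping only the two compared labels gave 4.4% to 5.6% in every scenario. A studentised statistic under the same three-label shuffle gave 4.7% to 5.6%.

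**Power for IFG versus sham.**

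- ρ = 0.5, IFG effect 0.5 SD (75% power with pair-only swapping): about 66% if the SMG effect is 1.0 SD and 46% if it is 1.5 SD.
- ρ = 0, IFG effect 0.8 SD: 73.8% with three labels against 84.5% pair-only if the SMG effect is 1.6 SD.
- ρ = -1/3, IFG effect 0.8 SD: 72.9% against 72.5% if SMG equals sham, and 72.7% against 73.4% if SMG equals IFG. There is no material difference in either case.

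**The case against.** The strongest reply has five parts.

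- **The statistic is open.** The level problem needs an unstudentised mean difference, and the plan does not say that is what is permuted. This stands: a studentised version of the same shuffle is sound. It makes the point conditional but does not remove it, because nothing in section 6c leads a programmer to studentise.
- **Mean shifts err on the safe side.** With equal spread, an effect at the other site only lowers the level. This stands; the cost is power. Inflation needs a clearly less variable and little-shifted third condition, and the documents give no reason to expect one.
- **Large losses need lopsided effects.** The falls to 66% and 46% require the other site's effect to be two or three times as large, at a correlation of 0.5 that does not match the plan's design effect. This stands as a limit on size.
- **The second site is optional.** The Analyses section and the Table 1 example use full treatment blocks of IFG and sham only. With two conditions the swap is already pair-only. This stands.
- **Pair swapping does not mirror the randomisation either.** Only three of the six orders are assigned. Swapping IFG and sham in SMG–sham–IFG gives SMG–IFG–sham, which no patient can receive. True, but it applies to both shuffles and is a separate matter; the simulations here contain no period effects.

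A reader might infer that neither pairwise test holds its 5% level, or that the primary analysis inflates false positives. The documents support neither. Both tests hold their level if the three conditions are alike. If only one site works, that site's null is false, so only the other site's level is affected, and with equal spread it falls.

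**Conclusion.** The point holds as a conditional one. When a second site is used, the stated rule tests each pair against a null of global equality. With a raw mean difference, the level and power of each comparison then depend on the other site. The level is about 5% if all three conditions are alike, about 1% to 3% for a 1 SD shift with equal spread, and about 7% to 9% only if the third condition is clearly less variable and little shifted.

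These figures rest on assumed values for alpha, SDs and correlation, on normal change scores and on an unstudentised statistic. The direction of the error in this trial cannot be known from the documents. The stated 75% power reproduces and is not challenged. The matter still goes beyond missing detail: the shuffle that is written down does not correspond to the pairwise hypotheses it is meant to test, and this is the primary analysis.

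**What to change.** Change section 6c so that, for each pairwise hypothesis, only the two labels being compared are permuted within each patient (IFG with sham, or SMG with sham) and the third condition is left out of that test. Alternatively, keep the three-label shuffle and specify a studentised statistic. In either case, name the statistic, the significance level and the sidedness. Retain the three-label permutation of the raw difference, if wanted, only as a global test that any condition differs.

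The cost is a sentence or two in section 6c and a small change to the program. It needs no new data or patients, and in the scenarios examined it costs no material power.
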